3.4 Withdrawal Criteria

Consenting parents/legal guardians will be informed that they have the opportunity of withdrawing their infant/s from the study at any time with no explanation. Data generated by the drawn infant/s will be censored at the time of withdrawal. They will remain part of the study and will be analyzed by intention to treat and per-protocol approach for adherent patients to their protocol. Withdrawn children who require ongoing supplemental oxygen will receive the standard care for bronchiolitis, and no additional data will be collected after withdrawal.

[figure not shown]

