7.2 Data Analysis Methods

Categorical and continuous variables will be expressed as frequency (percentage) and median (IQR). Between groups, we will use the Mann-Whitney-U test for comparing the time of success for HR, RR, and CRS (SPSS Inc., version 25.0, Chicago, IL, USA). The longitudinal analysis part of the study will be performed non-parametrically with the Brunner Langer model for CRS conducted with a linear mixed model in a parametric way for HR and RR. Brunner Langer model (F1-LD-F1) is applied using web-based software (R software, version 3.5.2, package: nparLD, R Foundation for Statistical Computing, Vienna, Austria; <http://r-project.org>). The PROC MIXED procedure in the SAS software is used (Version 9.3; SAS Institute, Cary, NC, USA) to perform linear mixed models in which subjects will be included as random effects. When there is a significant interaction effect in the longitudinal analysis ($P < .1$), the time effect will be analyzed in each group, and groups will be compared at baseline and following time points (the baseline was subtracted from these time points). The proportions of the treatment failure at 4 hours, rescued patient, ICU admission, and AE are analyzed using Fisher's Exact test and given with odds ratio (OR) and 95% Confidence Interval (CI). We will perform intention-to-treat and per-protocol approaches for all outcomes. The time of success for HR, RR, and CRS outcomes will be analyzed using the PP approach. A 2-sided $P < .05$ defines statistical significance.

Statistical Analysis Plan

The biostatistician in the study, which has blinded to allocation, will perform the analysis. An interim analysis will not be performed. If substantial evidence of increased risk of harms ($p < 0.001$) observed in both groups, stopping rules will be used with the biostatistician's advice. Intention to treat and per-protocol approaches will be conducted if necessary.

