9. STUDY ADMINISTRATION

9.1 Protocol Deviations

Protocol deviations will be reported in the publication of the results (CONSORT, 2010).

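### The plan gives conflicting analysis sets for the three primary recovery times, does not define per-protocol, and plans a test that cannot use the times of withdrawn children

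*Combined protocol and SAP*

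**What the plan says.** Section 2.2 makes the times for HR, RR and CRS to improve, in hours, the primary outcomes. Four statements bear on who is analysed:

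- Section 7.2: "We will perform intention-to-treat and per-protocol approaches for all outcomes".
- Section 7.2, next sentence: "The time of success for HR, RR, and CRS outcomes will be analyzed using the PP approach".
- Statistical Analysis Plan paragraph at the end of section 7: "Intention to treat and per-protocol approaches will be conducted if necessary". No condition is given.
- Section 3.4, on withdrawn children: they stay in the study and are "analyzed by intention to treat and per-protocol approach for adherent patients to their protocol".

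That last phrase is the only description of PP. Section 9.1 says that deviations will be reported, not which of them exclude a child.

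On the test, section 7.2 says "we will use the Mann-Whitney-U test for comparing the time of success for HR, RR, and CRS". On withdrawal, section 3.4 says "Data generated by the drawn infant/s will be censored at the time of withdrawal", and collection of data then stops. No survival method, rank rule or imputation is given for a child whose recovery was not observed.

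**The concern.** Two analysts following this text could produce different primary results. One could lead with all children as allocated, the other with PP, and they could classify the same rescued child differently. The trial is open-label (section 3.6), so these choices could be made with outcomes in view.

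Which children leave PP matters because failure is tied to the outcome. If failures are dropped and are more common on St-FMOT, the slower children leave mainly that arm. All three comparisons then shift towards St-FMOT, even if recovery is the same.

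The withdrawal gap is separate. A child withdrawn before recovery has an unknown recovery time. A Mann-Whitney test must either omit the child or be given an invented value, and the plan does not say which.

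**Working it through.** **1. The texts side by side.** The first 7.2 sentence names both sets without condition, the second names PP alone for the recovery times, and the SAP paragraph makes both conditional. The first two can be read as both sets with PP leading, but the text does not say so. The third still contradicts the first.

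**2. Failure and the outcome.** Section 5.3 needs at least three of five criteria. Three are non-improvement in HR, RR or CRS; two are SpO₂ and carbon dioxide. At most two of the three required can be other variables, so at least 3 − 2 = 1 is a primary variable. This needs no assumption.

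**3. The plan's own figures (section 7.1).** 100 × 1.10 = 110 reproduces the final size; 100/0.90 = 111.1, or 112 in equal arms, is close. The totals 100, 43 and 38 cannot be checked, because no difference or SD is given. Solved backwards (two-sided t-test, alpha 0.05, power 80%, non-centrality d√N/2), they imply:

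- CRS, N = 100: d = 0.566
- HR, N = 43: d = 0.875
- RR, N = 38: d = 0.934

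**4. Scale of the CRS effect.** The documents do not say whether 0.566 is in SDs of hours or of log hours. For log-normal times with log SD 1, SD/mean = √(e − 1) = 1.311. If 0.566 is in pooled raw-hour SDs, the ratio of means r solves (1 − r)/(1.311 × √((1 + r²)/2)) = 0.566. This gives r ≈ 0.43, a log effect of about 0.85.

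**5. If failures are dropped from PP (simulation).** All rates are assumptions.

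- 50 per arm; log-normal times, control median 24 h, log SD 1.
- Times rounded up to the scheduled visits, then daily to 240 h.
- Failure correlated 0.5–0.8 with slow recovery; tie-corrected Mann-Whitney test.
- 20,000 trials per scenario for the null ranges, 6,000 for the raw-hour comparison.
- The null ranges at unequal rates also span control medians of 12–48 h and log SD 0.7–1.3.

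| Failing, St-FMOT v HFNCOT | No true difference: PP favours St-FMOT (nominal 2.5%) | CRS power, log-SD effect: PP (all children) | CRS power, raw-SD effect: PP (all children) |
|---|---|---|---|
| 10% v 10% | about 2.5% | 75–80% (76%) | about 98% (98%) |
| 10% v 5% | 4–5% | 67–70% (76%) | about 97% (98%) |
| 20% v 8% | 6–11% | about 55% (76%) | about 93% (98%) |

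At 20% v 8% with correlation 0.65, equal true medians of 24 h become about 20 h v 22 h in PP.

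**6. Withdrawal (simulation, 55 per arm, no true difference).** At 10% v 10% withdrawn, dropping them, entering the last assessment as a success and Gehan-Wilcoxon all keep 2.4–2.7% error per side. At 15% v 5%, results falsely favour St-FMOT in 2–10% of trials if withdrawn children are dropped and 9–13% if the last assessment is entered as a success. Gehan-Wilcoxon gives 1.4–3.4% for St-FMOT and 1.6–3.9% for HFNCOT.

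**The case against.** Four points deserve weight.

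- **Both sets are promised.** Section 7.2 and section 3.4 name intention-to-treat, so it will probably be reported. That stands: a reader might infer that the primary times will be analysed by PP alone, and the documents do not support so firm a reading. They leave the order of the two sets open.
- **Rescue may count as adherence.** Section 5.3 makes it a protocol step, so a rescued child may belong in PP. That also stands. Exclusion is one reading, and every figure in step 5 depends on it. The 20% v 8% null case is strained as well, because it assumes very different failure rates alongside identical recovery.
- **The loss of CRS power may be small.** It is large on the log scale and slight on the raw-hour scale. A reader might infer that the PP sentence would hide a real CRS benefit, but the documents do not give the scale, so this cannot be claimed.
- **Censoring in section 3.4 may only mean that data collection stops.** Possibly, but the recovery time of a child withdrawn before recovery is then still unknown and has no rule.

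Two further inferences should be avoided. Non-recovery at 96 h is not a gap, because the schedule continues procedures beyond 96 h and the CRF runs to day 10. Nor does any section say that ICU transfer ends measurement.

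The SAP's blinded biostatistician helps little. Ward rescue with HFNCOT exists only in the control arm, so a record of it reveals the allocation.

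**Conclusion.** The point holds and must be fixed before analysis. It rests on the text: conflicting sets, no primary set, no criteria for PP, and a test that cannot take the times section 3.4 leaves incomplete. Confidence in this is high.

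The size is conditional. With equal failure rates there is no bias. If failures are excluded, one-sided error towards St-FMOT rises modestly at 10% v 5% and more clearly at the illustrative 20% v 8%. The false-positive figures do not depend on the scale of the planned effect; the CRS power figures do. The documents give no failure, rescue or withdrawal rates by arm, so the actual bias is unknown.

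**What to change.** **Wording to adopt**

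1. The primary analysis of all three times includes every allocated child in the allocated arm, with ward-rescued children kept at their observed time.
2. PP is a sensitivity analysis, with a listed set of exclusions that says whether rescue is one.
3. Delete the sentence naming only PP for the recovery times, and the conditional wording in the SAP paragraph.
4. Replace the Mann-Whitney test with Kaplan-Meier medians and a Gehan-Wilcoxon test, which equals Mann-Whitney when no child is censored. Censor withdrawn children at their last assessment.
5. Declare before analysis how three cases are handled: ICU transfer, discharge before success, and a value already normal at entry (section 3.2 requires neither HR nor RR to be abnormal).

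The rules under item 5 are the sponsor's choice, and each has a cost. Worst rank for ICU transfer weighs on the arm that section 5.3 sends directly to ICU. At 10% v 10% failing on the log scale, it gave CRS power of about 53%, against 78% for PP without failures. Censoring at transfer or at discharge may be informative. At least one alternative should therefore be a sensitivity analysis.

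**Cost.** SAP text and standard software. Dates of withdrawal, rescue and transfer must come from the chart, because the CRF records 4-hour failure and ICU transfer only as yes/no. Rescue has to be captured anyway: "The proportions of the treatment failure at 4 hours, rescued patient, ICU admission, and AE are analyzed". Gehan-Wilcoxon carries a small bias if withdrawal differs between arms, as step 6 shows.

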2. STUDY OBJECTIVE

2.1 Study Question

In children aged between 1 and 24 months with moderate and severe bronchiolitis requiring oxygen supplementation, does HFNCOT delivered via a Fisher & Paykel MR850 humidifier with Optiflow Junior prongs compared to St-FMOT decrease HR, RR, and CRS during the acute admission?

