2.2 Primary Objectives

- ✓ The median time it takes for HR to reach its normal range for age (hour)
- ✓ The median time it takes for RR to reach its normal range for age (hour)
- ✓ The median time it takes for CRS to regress from severe [scores of 9-12] to moderate [scores of 5-8] bronchiolitis, or from moderate [scores of 5-8] to mild [scores of 0-4] bronchiolitis (hour)

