7. STATISTICAL METHODS

7.1 Sample Size

Sample size calculations were done using a t-test on the primary outcome. Based on our pilot trial to obtain a power of 80% and alpha of 0.05 with a 1:1 proportion of control to intervention groups, the sample size yielded a total of 100 participants for CRS, 38 for RR, and 43 for HR. Given these sample sizes, we chose to recruit a minimum of 100 subjects. However, the final sample size was 110 patients, considering the study's longitudinal aspect (with a 10% attrition rate).

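### Three unranked primary outcomes and no success rule: if any one P<.05 may count, the chance of a false significant result in either direction is up to 14.3%, not 5%

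*Combined protocol and SAP*

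**What the plan says.** Section 2.2 Primary Objectives and the Study Synopsis list three primary outcomes: the time for HR to reach its normal range for age, the same for RR, and a third described as "The median time it takes for CRS to regress from severe [scores of 9-12] to moderate [scores of 5-8] bronchiolitis", or from moderate to mild. The synopsis numbers them 1 to 3, but nothing makes that a testing order.

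Section 7.2 Data Analysis Methods gives the test, "we will use the Mann-Whitney-U test for comparing the time of success for HR, RR, and CRS", and the criterion, "A 2-sided $P < .05$ defines statistical significance".

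Other passages point in different directions on how the three combine:

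- Section 2.1 Study Question names them jointly, asking whether high-flow oxygen does "compared to St-FMOT decrease HR, RR, and CRS during the acute admission".
- Section 7.1 Sample Size speaks of one outcome: "Sample size calculations were done using a t-test on the primary outcome".
- The same section then sizes all three at alpha 0.05 and 80% power: "the sample size yielded a total of 100 participants for CRS, 38 for RR, and 43 for HR". It takes the largest.

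The part of section 7.2 headed Statistical Analysis Plan covers blinding of the biostatistician, the absence of an interim analysis, stopping for harm, and the intention-to-treat and per-protocol approaches. Neither it nor any other section gives an adjustment, a testing order or a success rule.

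**The concern.** A trial with several primary outcomes needs a stated rule linking the individual tests to the conclusion, because the rule fixes the error rate. Here the rule is missing. As written, one significant result out of three could be reported as a positive primary finding, and so could two or three. A reader could not tell whether the conclusion carries an error rate of at most 5% or something nearer 14%. The rule could also be settled after the results are known. That matters more in an open-label trial in which section 7.2 first promises both intention-to-treat and per-protocol analyses for all outcomes and then names per-protocol for these three.

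**Working it through.** **Inputs from the documents.** Three primary tests (2.2, 7.2); two-sided 0.05 for each (7.2); total sizes of 100 for CRS, 38 for RR and 43 for HR at 80% power by t-test with 1:1 allocation (7.1); 110 recruited after a 10% attrition allowance (7.1). The correlation between outcomes is not given, so a range is assumed.

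**The plan's own figure.** 100 × 1.10 = 110, which matches. Dividing instead, 100 / 0.90 = 111.1, or 112 in two equal arms; the difference is immaterial here. The sizes of 100, 38 and 43 cannot be rebuilt, because no effect size or SD is stated.

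**Error rate if all three are required.** The chance that all three are significant cannot exceed the chance that any given one is, so it is at most 5%.

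**Error rate if any one is enough.**

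- Independent tests: 1 − (1 − 0.05)³ = 1 − 0.857375 = 14.26%.
- Favouring high-flow oxygen only: 1 − (1 − 0.025)³ = 7.31%.
- Bound under any dependence: 3 × 0.05 = 15.0% in either direction, and 3 × 0.025 = 7.5% for benefit.
- Equal correlation ρ between jointly normal test statistics: 1 − ∫ [Φ((1.96 − √ρ·u)/√(1−ρ)) − Φ((−1.96 − √ρ·u)/√(1−ρ))]³ φ(u) du. The one-direction version drops the second Φ.

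| Assumed ρ | Either direction | Favouring high-flow |
|---|---|---|
| 0 | 14.26% | 7.31% |
| 0.3 | 13.62% | 6.83% |
| 0.5 | 12.54% | 6.27% |
| 0.7 | 10.92% | 5.46% |
| 0.8 | 9.82% | 4.91% |
| 0.9 | 8.36% | 4.18% |

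The inflation disappears only at ρ = 1. Some positive correlation is likely, because respiratory rate is one of the four CRS items (Appendices 1).

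**Does the grouping of times by visit change this?** I simulated Mann-Whitney tests with a tie correction, using lognormal times (assumed median 12 h, log-SD 1.2) rounded up to the scheduled visits from 1 to 96 h, with 50 per arm. The any-one error was about 14%, 12–13%, 11% and 9% at assumed child-level correlations of 0, 0.5, 0.7 and 0.9. The normal-theory figures are a fair guide.

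**Power under each rule.** Solving the t-test for 80% power at the stated totals gives standardised effects d = 0.566 (CRS), 0.934 (RR) and 0.875 (HR). With 50 evaluable per arm, the expected test statistic is d × √(50/2) = 5d. For CRS that is 2.83, so unadjusted power by normal approximation is Φ(2.83 − 1.96) ≈ 81%. RR and HR come to about 99.7% and 99.2%. An all-three rule with independent tests therefore has 0.807 × 0.997 × 0.992 ≈ 80% power.

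Holm compares the smallest P value with 0.05/3 = 0.0167, the next with 0.025 and the largest with 0.05, stopping at the first failure. Simulation with the CRS effect fixed and ρ from 0 to 0.7 gives:

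| RR and HR effects, as share of implied | CRS power lost under Holm (points) | Power of all-three rule |
|---|---|---|
| 100% | 0.1–0.3 | 80–81% |
| 75% | 2–3 | 69–77% |
| 50% | 8–11 | 31–48% |
| none | about 14 | not applicable |

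Under Holm, RR and HR themselves lose up to about 1, 5 and 9 points in the first three rows.

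**The case against.** The documents never say that one significant outcome suffices, and some of the text leans the other way. If any one were enough, a total of 38 would already have given the stated power for RR; recruiting to the largest of the three sizes fits an all-three rule, or three separate claims, better. The study question is also worded jointly. On the reading of three separate claims, each carries its own 5% error, and whether a single-centre phase 4 trial then needs family-wise control is partly a matter of judgement. Finally, 14.3% assumes independence, which is unlikely here, and it counts false results favouring the face mask.

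Much of this is fair. The 14.3% is a ceiling for jointly normal statistics, not an estimate, and it applies to one reading only. But choosing the largest size secures power for each outcome; it does not define success. Nothing in the text prevents a single significant outcome from being presented as the primary result. Allowing for correlation does not rescue that reading either: at an assumed 0.9 the rate is still 8.4%, and in the benefit direction 4.2% against 2.5%.

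The power figures have a limit of their own. They assume 50 evaluable per arm, whereas the primary times are analysed per protocol. If children who receive rescue treatment leave that set, which the documents do not settle, power is lower under every rule.

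**Conclusion.** The concern holds. The plan has three unranked primary outcomes, an unadjusted two-sided 0.05 for each, and no success rule, so the error rate of the overall primary claim is not defined. It is at most 5% if all three are required. If any one suffices, it runs from 8.4% to 14.3% in either direction, and from 4.2% to 7.3% in favour of high-flow oxygen, over assumed correlations of 0.9 down to 0. Those figures rest on jointly normal test statistics with equal correlation and one analysis per outcome. Counting either the intention-to-treat or the per-protocol result would push the any-one rate higher. This should be fixed: it bears on the main conclusion, and the repair is small.

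**What to change.** State the success rule in section 7.2 and choose one of two forms.

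1. **Any one outcome may support a claim.** Add: *The three primary outcomes are tested with the Holm procedure at a family-wise two-sided alpha of 0.05.* Report Holm-adjusted P values, and name the analysis set for these tests in the same sentence.
2. **All three are required.** Add: *The trial is positive only if HR, RR and CRS recovery times are each significant at two-sided P<.05.* No adjustment is then needed.

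If outcomes have already been compared by arm, label the rule post hoc and report unadjusted and Holm-adjusted P values for all three.

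The cost is one sentence and no extra patients. The price in power depends on the RR and HR effects: Holm is almost free at the implied effects but takes 8–11 points from CRS if those effects are half as large, while the all-three rule then falls to 31–48% power. Plain Bonferroni is the poorer choice. At 0.0167 per test, CRS power is about 65% with 50 per arm, and restoring 80% would take about 67 per arm, or 134 / 0.90 ≈ 149 in total.

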8. REGULATORY CONSIDERATIONS

8.1 Participant Consent

We will describe the study's nature and identified risks to the parents/legal guardians of possible recruits in a written document (Informed Volunteer Consent Form) and verbally. An Investigator will obtain written informed consent from each participant's parent/legal guardian before participation in the study under regulatory requirements.

8.2 Ethical Review

Before the study's commencement, the protocol and any amendment(s), Informed Consent Form, and Study Information Letter will be referred to the HREC of EUMF, and the Principal Investigator will keep the written approval. The approval will submit to the study by title, protocol number, and version date and provide details of the documents reviewed by the HREC. During the course, the Principal Investigator will submit to the HREC: amendments to the protocol, adverse event data, outcome, and administrative changes to the protocol. At the end of the study, the Principal Investigator will inform the HREC in writing that the course has ended. No further activities regarding this protocol will be conducted at the site. The Investigators will perform the above responsibilities under the Note for Guidance on Good Clinical Practice annotated with any adverse events comments and the National Health and Medical Research Council National Statement on Ethical Conduct in Human Research, 2008.

8.3 Sponsor

The Director of the Scientific Research Projects of Ege University will approve the study. There is no other sponsor. Material for the trial is supplied under the Ministry of Health contract arrangements and loan items from Fisher and Paykel®.

9. STUDY ADMINISTRATION

9.1 Protocol Deviations

Protocol deviations will be reported in the publication of the results (CONSORT, 2010).

9.2 Monitoring and Auditing

Researchers will meet periodically to discuss the trial progress and review processes. The team will analyze adverse events as they are notified.

9.3 Study Documentation and Records Retention

Pediatric study documentation will be kept for a minimum of 22 years. Participant files and other essential documents (study protocol, signed informed consent forms, correspondence, and other documents relating to the study) will be securely archived in HREC of EUMF to meet these conditions. He or she must notify the Study Approver if the Researcher should want to assign the investigation documentation to another party or transfer to another position.

9.4 Publication and Use of Study Findings

Study findings will be submitted to various peer-reviewed, high impact journals depending on the report's focus, e.g., pediatric diagnostics, pathology, and respiratory disease.

10. Appendices

Appendices 1: Initial Assessment of Children According to CRS Reported by Liu and Colleagues.

	0 point	1 point	2 point	3 point
Respiratory rate				
<2 months		≤60	61–69	≥70
2-12 months		≤50	51–59	≥60
1-2 years		≤40	41–44	≥45
2-3 years		≤34	35–39	≥40
4-5 years		≤30	31–35	≥36
6-12 years		≤26	27–30	≥31
>12 years		≤23	24–27	≥28
Retraction	None	IC	IC and SS	IC, SS, and SC
Dyspnea				
0-2 years	Normal feeding, vocalizations, and activity	1 of the following: difficulty feeding; decreased vocalization; or agitated	2 of the following: difficulty feeding; decreased vocalization; or agitated	Stops feeding, no vocalizations, or drowsy or confused
2-4 years	Normal feeding, vocalizations, and play	1 of the following: decreased appetite, increased coughing after play, hyperactivity	2 of the following: decreased appetite, increased coughing after play, hyperactivity	Stops eating or drinking, stops playing, or drowsy or confused

≥5 years	Counts to ≥ 10 in one breath	Counts to 7–9 one breath	Counts to 4–6 in one breath	Counts to ≤ 3 in one breath
Wheeze	Normal breathing; no wheezing present	End-expiratory wheeze only	Expiratory wheeze only (greater than end-expiratory wheeze)	Inspiratory and expiratory wheeze or diminished breath sounds or both

Appendices 2: Parent Follow up Questionnaire

Appendices 3: Pediatric Early Warning Score

	Age groups	0	1	2	4
Heart rate (bpm)	0 to < 3 months	> 110 and < 150	≥ 150 or ≤ 110	≥ 180 or ≤ 90	≥ 190 or ≤ 80
	3 to < 12 months	> 100 and < 150	≥ 150 or ≤ 100	≥ 170 or ≤ 80	≥ 180 or ≤ 70
	1-4 years	> 90 and < 120	≥ 120 or ≤ 90	≥ 150 or ≤ 70	≥ 170 or ≤ 60
	>4-12 years	> 70 and < 110	≥ 110 or ≤ 70	≥ 130 or ≤ 60	≥ 150 or ≤ 50
	>12 years	>60 and < 100	≥ 100 or ≤ 60	≥ 120 or ≤ 70	≥ 140 or ≤ 40
Systolic blood pressure (mmHg)	0 to < 3 months	> 60 and < 80	≥ 80 or ≤ 60	≥ 100 or ≤ 50	≥ 130 or ≤ 45
	3 to < 12 months	> 80 and < 100	≥ 100 or ≤ 80	≥ 120 or ≤ 70	≥ 150 or ≤ 60
	1-4 years	> 90 and < 110	≥ 110 or ≤ 90	≥ 125 or ≤ 75	≥ 160 or ≤ 65
	>4-12 years	> 90 and < 120	≥ 120 or ≤ 90	≥ 140 or ≤ 80	≥ 170 or ≤ 70
	>12 years	> 100 and < 130	≥ 130 or ≤ 100	≥ 150 or ≤ 85	≥ 190 or ≤ 75
Capillary refill time		< 3 seconds			≥ 3 seconds
Respiratory rate (breaths/minute)	0 to < 3 months	> 29 and < 61	≥ 61 or ≤ 29	≥ 81 or ≤ 19	≥ 91 or ≤ 15
	3 to < 12 months	> 24 and < 51	≥ 51 or ≤ 24	≥ 71 or ≤ 19	≥ 81 or ≤ 15
	1-4 years	> 19 and < 41	≥ 41 or ≤ 19	≥ 61 or ≤ 15	≥ 71 or ≤ 12
	>4-12 years	> 19 and < 31	≥ 31 or ≤ 19	≥ 41 or ≤ 14	≥ 51 or ≤ 10
	>12 years	> 11 and < 17	≥ 17 or ≤ 11	≥ 23 or ≤ 10	≥ 30 or ≤ 9
Respiratory effort		Normal	Mild increase	Moderate increase	Severe increase/any apnea
Oxygen saturation (%)		> 94	91 to 94	≤ 90	

Protocol No 1
Date: 10/03/2017
Revised 1: 10/03/2020
Revised 2:14/02/2021

Oxygen therapy		Room air		Any to < 4 L/minute or < 50%	≥ 4 L/minute or $\geq 50\%$
-----------------------	--	----------	--	------------------------------	----------------------------------

Appendices 4. Case report form

Case No and date								
Age (months)								
Gender	 Male		 Female					
Gestational age								
Body weight (gr/kg)								
Virus detected in RT-PCR	 Yes		 No					
If yes, which virus was detected								
Number of bronchiolitis	 1		 2		 3+			
Season	 Winter		 Autumn		 Spring		 Summer	
Study device	 St-FMOT  HFNCOT							
VARIABLES	Body temperature (°C)	Heart rate (bpm)	Respiratory rate (/min)	Arterial tension (mm/Hg)	SpO ₂ (%)	Venous blood gases	Ph-PCO ₂	CRS
At first admission								
1 h								
2 h								
4 h								
12 h								
24 h								

2 d							
3 d							
4 d							
5 d							
6 d							
7 d							
8 d							
9 d							
10 d							
Length of oxygen requirement (h)							
Length of hospital stay (d)							
Beta2 mimetic use?	 Yes		 No				
If yes, how many days did it use? (d)							
Inhaler corticosteroid use?	 Yes		 No				
If yes, how many days did it use? (d)							
IV corticosteroid use?	 Yes		 No				
If yes, how many days did it use? (d)							
Inhaler hypertonic saline use?	 Yes		 No				
If yes, how many days did it use? (d)							
Did any complications occur?	 Yes		 No				

Which complications occurred?			
